### 7.4.3 Analysis of Key Secondary Efficacy Endpoints

If the null hypothesis for the primary endpoint is rejected, the statistical tests on the key secondary endpoints across all five post-surgical time points will be performed using the serial gatekeeping procedure known as Hochberg's step-up method.

For the key secondary efficacy endpoint of proportion of subjects who achieve a pain score of 0 on the VAS, the difference between the treatment groups at each post-surgical assessment will be tested using a two-sided Z-Test with continuity correction and pooled variance. Missing values will be imputed using the LOCF method. Hochberg's method will be applied to the ordered p-values from these tests across the five time points. A 95% CI for the difference of the proportions at each time point will also be constructed. The effect of imputing missing values for this secondary endpoint analysis of proportions using the LOCF method will be assessed via a multiple imputations procedure.

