### 4.2 Key Secondary Endpoints

The secondary efficacy endpoints are the proportion of subjects who achieve a pain score of 0 on the visual analog scale (VAS) (0-100 mm scale) for each post-surgical assessment at Days 1, 8, 15, 18, and 29.

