## **7.0 STATISTICAL METHODS**

### **7.1 General Statistical Conventions**

All statistical procedures will be completed using SAS version 9.4 or higher.

Unless otherwise specified, all statistical hypothesis testing for the primary and secondary efficacy endpoints will be two-sided and will be performed using a significance (alpha) level of 0.05. Two-sided 95% confidence intervals (CI) will be provided when relevant.

For categorical variables, summaries will include counts of subjects (frequencies) and percentages. Percentages will be rounded to one decimal place.

For summary purposes, baseline will be defined as Visit 1, the screening visit value; all summaries will be presented by treatment group, unless otherwise specified.

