#### **7.4.1.2 Multiplicity**

Multiplicity adjustments will control the overall type I error rate at 0.05 for testing two treatment groups and multiple endpoints.

Among the primary and key secondary endpoints, the tests will be performed using a serial gatekeeping procedure based on the hierarchical order of the primary and key secondary endpoints. Therefore, the statistical tests on the key secondary endpoints across all five postsurgical time points will only be performed in case the null hypothesis for the primary endpoint is rejected.

The following multiplicity adjustment will be used to strongly control the overall type I error rate at 0.05 for the key secondary endpoints at each assessment. Multiplicity will be addressed via Hochberg's step-up method.

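### Hochberg's step-up for the five pain tests is valid, but Hommel's procedure needs the same condition, loses no claim and adds up to about one point of power per time point

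*SAP*

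**What the plan says.** SAP 4.2 defines the key secondary endpoint as the proportion of subjects with a VAS pain score of zero "for each post-surgical assessment at Days 1, 8, 15, 18, and 29", which makes a family of five hypotheses. SAP 7.4.1.2 places the family behind the primary endpoint: the five tests "will only be performed in case the null hypothesis for the primary endpoint is rejected". Within the family, "Multiplicity will be addressed via Hochberg's step-up method", and the adjustment "will be used to strongly control the overall type I error rate at 0.05 for the key secondary endpoints".

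SAP 7.4.3 adds that the difference at each assessment "will be tested using a two-sided Z-Test with continuity correction and pooled variance. Missing values will be imputed using the LOCF method", and that Hochberg's "method will be applied to the ordered p-values from these tests across the five time points". SAP 7.1 sets the general rule that tests "will be two-sided and will be performed using a significance (alpha) level of 0.05". Protocol 2.0 and SAP 3.1 give 160 subjects on ISV-305 and 80 on vehicle.

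Neither document mentions Hommel's procedure or claims that Hochberg's is the most powerful choice. The text gives no power target, expected pain-free rate or correlation between visits for these endpoints.

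**The concern.** Hochberg's rule compares each ordered p-value with one fixed cut-off. It is a conservative shortcut to the closed test that applies the Simes test to every intersection of hypotheses. Hommel's procedure carries out that closed test in full. Both rely on the Simes inequality, so the strong control that the SAP claims carries over without a new assumption.

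The two can differ when several p-values are moderately small and close together and at least one exceeds 0.05. Repeated pain assessments in the same subjects can plausibly produce that pattern. The five gated tests are the only efficacy tests of pain in the SAP, and pain is named in the trial's title. What is at stake is a small amount of power for pain claims at individual time points, which the plan could have at no cost.

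**Working it through.** **Inputs from the documents.** Five hypotheses (SAP 4.2); familywise two-sided 0.05 (SAP 7.1 and 7.4.1.2); continuity-corrected pooled Z-test (SAP 7.4.3); 160 versus 80 subjects (SAP 3.1). Pain-free rates and correlations are assumptions.

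**The two rules.** Order the p-values p(1) ≤ … ≤ p(5).

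- Hochberg: find the largest i with p(i) ≤ 0.05/(6 − i) and reject H(1) to H(i). From the largest p to the smallest, the cut-offs are 0.05, 0.025, 0.0167, 0.0125 and 0.01.
- Hommel: find the largest j for which p(5 − j + k) > k × 0.05/j for every k = 1, …, j. If there is no such j, reject all five. Otherwise reject every hypothesis with p ≤ 0.05/j.

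**Hommel loses nothing.** Suppose Hochberg rejects up to i, so p(i) ≤ 0.05/(6 − i). For any j = 6 − i + m with m ≥ 0, p(i) is compared with 0.05 × (1 + m)/(6 − i + m), which is at least 0.05/(6 − i). So p(i) does not exceed it, and that j fails. Hence j ≤ 5 − i, or no j exists. Hommel's cut-off 0.05/j is then above p(i), and H(1) to H(i) are all rejected. On 3,000 random sets of p-values Hommel kept every Hochberg rejection and added at least one in 5.4%.

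**All five.** Both procedures reject all five exactly when p(5) ≤ 0.05, so they do not differ there.

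**Example.** Take p = 0.011, 0.024, 0.029, 0.039, 0.20.

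- Hochberg: 0.20 > 0.05, 0.039 > 0.025, 0.029 > 0.0167, 0.024 > 0.0125, 0.011 > 0.01. No claim.
- Hommel: j = 5 fails because 0.029 ≤ 3 × 0.05/5 = 0.03. j = 4 holds: 0.024 > 0.0125, 0.029 > 0.025, 0.039 > 0.0375, 0.20 > 0.05. The cut-off is 0.05/4 = 0.0125, so there is one claim (0.011).

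**The plan's own figure, 0.05.** Familywise error with all five nulls true (2,000,000 draws of two-sided normal p-values, equal correlation):

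| Correlation | Hochberg | Hommel |
|---|---|---|
| 0 | 0.0490 | 0.0494 |
| 0.3 | 0.0469 | 0.0476 |
| 0.5 | 0.0423 | 0.0436 |
| 0.8 | 0.0313 | 0.0337 |

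With the SAP's continuity-corrected test, both are near 0.03 when all nulls are true and about 0.02 to 0.026 when only some are. The stated control holds for both.

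**Size of the gain.** 40,000 simulated trials per scenario with the planned test; vehicle rates 40% to 60%; the same difference at all five days, or a mixed pattern with an effect at only some days. Selected results:

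| Correlation | Difference | At least one claim: Hochberg → Hommel | Largest gain at one time point | Trials that differ |
|---|---|---|---|---|
| 0.5, equal | 10 points | 0.370 → 0.380 | 0.6 points | 2.0% |
| 0.5, equal | 15 points | 0.739 → 0.752 | 0.9 points | 3.4% |
| 0.5, equal | 20 points | 0.955 → 0.960 | 0.5 points | 1.9% |
| 0.5, equal | mixed | 0.684 → 0.691 | 0.5 points | 1.4% |
| 0.8, autoregressive | 15 points | 0.685 → 0.698 | 0.8 points | 3.2% |
| 0.8, autoregressive | 20 points | 0.929 → 0.936 | 0.6 points | 2.1% |

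Over all scenarios with an effect, the gain was 0.3 to 1.0 point per time point and 0.1 to 1.4 points for at least one claim, and 1.4% to 3.9% of trials differed. A wider scan of effect sizes, not tied to this trial's rates, reached 1.6 points for at least one claim.

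A second set used day-specific rates (for example vehicle/active 0.35/0.45 at Day 1 rising to 0.70/0.82 at Day 29) and correlations of 0.3 and 0.6. It gave 0.5 to 0.8 points per time point at Days 8 to 29, 0.1 to 0.5 at Day 1, and 0.4 to 1.2 for at least one claim.

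**In subjects.** For Hochberg to match Hommel's average power per time point, the sample size would have to grow by a factor of 1.0098 to 1.0186. That is 240 × 0.0098 ≈ 2.3 to 240 × 0.0186 ≈ 4.5 subjects.

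**The case against.** The strongest reply is that nothing here is wrong. Hochberg's method is standard, pre-specified and meets the SAP's stated control. The family, the gate, the test and the procedure are all fixed. No stated power figure is missed, because none is stated. Choosing one valid procedure over a slightly more powerful one is a matter of judgement, and the difference is worth two to four or five subjects. All of that stands, and it is why this is offered only as an improvement.

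Three stronger readings are tempting, and the documents support none of them.

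- A reader might infer that Hochberg fails to protect the error rate here. It does not: the simulated familywise error was at or below 0.049 in every case.
- A reader might infer that whole sets of pain claims are at risk. One can construct p = 0.012, 0.018, 0.024, 0.030, 0.20, where Hochberg claims nothing and Hommel claims three (adjusted p-values 0.040, 0.045 and 0.048). In the day-specific scenarios a move from none to three or more occurred in only 0.02% to 0.07% of trials. A move from none to at least one occurred in 0.4% to 1.25%.
- A reader might take the SAP 7.4.3 wording that labels the step-up a gatekeeping procedure as evidence of a flaw. SAP 7.4.1.2 separates the gate from the step-up clearly enough to carry out the analysis. The label is a clerical slip with no bearing on power.

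It is also fair to say that Hommel's realised error rate is slightly higher than Hochberg's (0.0337 against 0.0313 at correlation 0.8). It spends a little more of the same 0.05 and does not exceed it.

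**Conclusion.** The point holds as an optional improvement. Under the Simes condition that the plan already relies on, Hommel controls the same 0.05, never loses a Hochberg rejection and occasionally adds one. At 160 versus 80 the benefit is about 1 point of power or less per time point, about 0.1 to 1.4 points for at least one pain claim, and none for all five. The two procedures agree in about 96% to 99% of trials.

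That Hommel rejects at least as much is a mathematical fact and needs no assumption about rates. The size of the gain does rest on assumed pain-free rates and correlations, but it stayed below 2 points over everything tried. The figures also leave out the primary-endpoint gate. Since the pain tests are run only after the primary succeeds, the unconditional gain can be no larger than stated.

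**What to change.** Before unmasking, replace Hochberg's step-up with Hommel's procedure at two-sided 0.05 across the five time points in SAP 7.4.1.2 and 7.4.3. Report Hommel-adjusted p-values for Days 1, 8, 15, 18 and 29. Keep the gate on the primary endpoint as it is. While those sentences are open, the label that equates the step-up with gatekeeping can be tidied, as a separate wording matter.

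The cost is a small wording change in the SAP and one option in the SAS multiplicity procedure, with no extra subjects, data or alpha. The only drawback is that Hommel's rule is harder to describe in words, and reporting adjusted p-values deals with that. If the sponsor prefers to keep Hochberg, the analysis remains valid.

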### 7.5 Safety Analyses

All definitions relative to safety endpoints are detailed in Section 6.1.2.

All the safety analyses will be based on the Safety population (treated subjects) and will be performed for all safety variables specified below.

All safety data will be summarized by treatment group.

No statistical test will be performed.

#### Adverse events

All Adverse events (AEs) will be coded by Primary System Organ Class (SOC) and Preferred Term (PT) according to the Medical Dictionary for Regulatory Activities (MedDRA®) Version 20.0 or higher.

In summaries by SOC and PT, adverse events will be sorted by decreasing frequency within each SOC and PT according to the alphabetically order of ISV-305 treatment group.

Only treatment-emergent AEs (TEAEs) will be summarized. An AE will be considered a TEAE if it occurs or worsens on or after receipt of the first dose of study drug. AEs will be presented by subject.

Details for imputing missing or partial start dates of adverse events are described in Section 6.2.2.

AE summary tables will be presented for TEAEs only and will include the following:

- All TEAEs
- Serious AEs/TEAEs
- TEAEs leading to death.

All TEAEs will be summarized by SOC, PT and treatment group using frequency counts and percentages (i.e., number and percentage of subjects with an event).
